## ABSTRACT

[figure not shown]
**Introduction:** Bariatric surgery is associated with a 2-fold increase in the concentration of serum bile acids (BA). In rodents, BA delivered to the ileum induces weight loss and improves glucose homeostasis. These results are mainly mediated by the BA receptor, GPBAR1 (also known as TGR5). We recently identified a GPBAR1 gene variant associated with lower BMI and food intake. It is unknown whether the bile acid pathway is altered in obesity.

**Hypothesis:** Our central hypothesis is that the bile acid pathway (fasting serum BA, C4, FGF-19, fecal 48h BA excretion) is altered in obesity resulting in reductions in satiety-related hormones, such as FGF-19, PYY, or GLP-1. Therefore, there is a critical need to understand the role of BAs in food intake and body weight regulation in obesity compared to health.

**Aim:** Thus, we propose one specific aim: To characterize the bile acid pathway, key elements of the enterohepatic bile acid regulation and incretin pathway in obesity compared to health (normal weight) at three different metabolic stages: 1) at baseline, 2) stimulated by 100 grams of fat diet (standard, validated diet for testing bile acids) and 3) on a low calorie diet with <3% weight loss.

**Experimental design:** We will screen up to 45 participants to accrue a total of 38 participants [ 14 individuals with normal weight (BMI 20-25), 24 individuals with obesity (BMI >30)] to compare bile acid pathway, key elements of the enterohepatic bile acid regulation and incretin pathway at three different metabolic stages: 1) at baseline, 2) on a 100 grams of fat diet, and 3) on a low calorie, low fat diet. Participants will be on each diet for 7 days prior to collection of samples; with one week on regular diet between the high fat/calorie diet and the low calorie diet. Fasting and postprandial blood samples will be used to analyze, metabolomics, PYY, GLP-1, FGF-19, C4, BA, and short-chain fatty acids (SCFA) on test days. Saliva sample will be collected for GI peptides and metabolomics. Visual analog scale (VAS) ratings of appetite and satiation will be recorded during the day (on the same days) every 15 minutes for the first 90 minutes, then every 30 minutes. On day 5 and 6 (48 hours), stool from every bowel movement will be collected for fecal BA, SCFA and microbiome. Participants will repeat the stool collection and above studies for a total of three times. On day 5 of 1st, 2nd and 4th week, participants will undergo a flexible sigmoidoscopy with biopsies.

**Fig 1. Bile Acid Pathway**

**Expected outcome:** It is anticipated that the data acquired will lead to future hypothesis-testing studies of the role and interaction of the BA pathway, microbiome and incretins that are critical to circumvent weight regain.

## INTRODUCTION

**Obesity** prevalence continues to increase worldwide and, in the United States, 69% of adults are overweight or obese. Estimated costs to the healthcare system are more than \$190 billion annually – 10 percent of the total health budget – according to the Centers for Disease Control and Prevention (CDC 2012). Obesity affects almost every organ system in the body and increases the risk of premature mortality. It is estimated that a man in his twenties with a BMI over 45 will have a 22% reduction (13 years) in life expectancy. Increased severity of obesity correlates with a higher prevalence of the associated comorbidities. Hence, obesity increases the risk of numerous diseases including type 2 diabetes mellitus (T2DM), hypertension, dyslipidemia, cardiovascular disease, and cancer.

Currently, the most effective **treatment for obesity**, metabolic syndrome and T2DM is bariatric surgery. The efficacy of bariatric surgery in obesity and T2DM treatment, when compared to caloric restriction, demonstrates that the mechanism on weight loss and reversal of insulin resistance and hyperglycemia exceeds the effect of diet restriction seen in duodenal switch or Roux-en Y gastric bypass (RYGB). However, bariatric surgery is invasive with high mortality and morbidity and cannot be considered a public health remedy to the current obesity epidemic. On the contrary, obesity treatment with intense lifestyle interventions (ILI) (defined as low calorie diet, physical activity, and behavioral therapy) result in a mild weight loss (approximately 3-5%) within the first 12 weeks followed by a slow and gradual weight regain and the individual presumption of “failure”. Physiological changes or adaptations to weight loss have a major effect on the failure of weight loss maintenance, thus impeding the health benefits associated with weight loss. These adaptations – “pro-orexigenic” – are presumed to be secondary to increased appetite, decreased satiation and decreased thermogenesis.

Recent advances in the **understanding of bariatric surgery** suggest that bile acids play a role in the surgery-related improvement of diabetic profile. RYGB is associated with doubling of the concentration of serum bile acids, and an increase in serum adiponectin and GLP-1. In rodents, BA delivered to the ileum induces weight loss and improves glucose homeostasis. These results are mainly mediated by the BA receptor, GPBAR1 (also known as TGR5). GPBAR1 stimulation results in a rapid increase in incretins, reduced appetite and improvement in insulin sensitivity.

**Bile acids** (BAs) are steroid-derived detergent molecules that are excreted by the liver and are responsible for emulsification of lipids in the small intestine, aiding in lipid digestion and absorption. The key components of the BA pathway (Fig 1) are: a) The hepatocyte synthesizes bile from cholesterol; 7-alpha-hydroxy-4-cholesten-3-one (C4) is a serum marker for bile acid synthesis in humans. C4, a precursor of cholic acid in the classic pathway of bile acid synthesis from cholesterol, correlates with the time-limiting enzymatic step catalyzed by 7-alpha-hydroxylase. b) Bile acids are excreted into the duodenum and form simple micelles or micelles incorporating phospholipids to absorb cholesterol through the brush border membrane of the small intestine. c) In the terminal ileum, bile is reuptaken by the apical  $Na^+$ -dependent bile salt transporter [ASBT or also called ileal BA transporter (IBAT)]. In the enterocyte, BA activates farnesoid X receptor (FXR) to synthesize fibroblast growth factor-19 (FGF-19), which initiates a negative feedback to decrease the synthesis of BA. d) Less than 5% of BA is not reabsorbed and is deconjugated and dehydroxylated by colonic bacteria into secondary BA and then excreted in the stool. e) The liver captures and recirculates more than 99% of bile acid, suggesting that “serum” bile acid is a fraction of the BA in the enterohepatic circulation. f) Additionally, BA activates the

[figure not shown]

Fig 2. Summary of actions of BAs in gut mucosa [18]

GPBAR1 receptor in the enteroendocrine L-cell which secretes GLP-1 to regulate food intake and glucose homeostasis. Interestingly, each step of the BA pathway can be measured in humans, non-invasively (Fig 1). Recently, we identified a GPBAR1 gene variant associated with lower BMI, higher satiation (reduced food intake) and higher GLP-1 concentration; and demonstrated that obesity is associated with decreased fasting fibroblast growth factor 19 (FGF-19), a surrogate of ileal BA reabsorption (Fig 2). Interestingly, in mice, the BA effect on GLP-1 secretion is blunted in absence of GPBAR1. The synthesis, secretion and regulation of incretin hormones GLP-1, PYY and OXM are controlled by enteroendocrine L-cells in the small intestine and colon.

In summary, it is unknown whether 1) the bile acid pathway is altered in obesity and/or 2) it adapts to weight loss induced by diet only. Thus, there is a ***critical need to understand*** the role of BAs in food intake, absorption of lipids and body weight regulation in obesity compared to health. ***Our central hypothesis is that the bile acid pathway (fasting serum BA, C4, FGF-19, fecal 48h BA excretion) is altered in obesity resulting in reductions in satiety-related hormones, such as FGF-19, PYY, or GLP-1.*** Thus, there is a critical need to understand the role of BAs in food intake and body weight regulation in obesity compared to health.

The understanding of this mechanism will enhance our knowledge about the role of bile acid metabolism and pathway in obesity. Specifically, we hypothesize that the BA pathway –serum BA, FGF-19, GLP-1, PYY, and C4; fecal BA, and fecal microbiome – adapt to a pro-orexigenic mode after diet-induced weight loss to enhance food intake.

## INNOVATION

***The role of the bile acid pathway in obesity and the metabolic adaptation to weight loss:*** The outcome of these studies will contribute to the essential understanding of the role of the bile acid pathway in weight loss in humans. Usually, the components of the bile acid pathway are studied independently based on the strengths of each laboratory; for example, study of only “serum” BA”. Here, relying on support from the grant mentor, [name], we have assembled a team to study the whole BA pathway in humans under different interventions. The results will have a robust impact on the BA field and potential applications to obesity and diabetes treatment. Furthermore, the *in-unison* study will contribute to the reveal of a real-time sequence of events regulating or modulating the BA pathways and enterohepatic circulation. This type of analysis in BA physiology and obesity is novel and critically needed, especially with the notion that many BA pathway modulators are under development.

## APPROACH

***Our central hypothesis is that the bile acid pathway (fasting serum BA, C4, FGF-19, fecal 48h BA excretion) is altered in obesity resulting in reductions in satiety-related hormones, such as FGF-19, PYY, or GLP-1.*** This central hypothesis will be investigated in one specific aim: To characterize the bile acid pathway, key elements of the enterohepatic bile acid regulation and incretin pathway in obesity compare to health (normal weight) at three different metabolic stages: 1) at baseline, and either 2) stimulated by 100 grams of fat diet (standard, validated diet for testing bile acids) or 3) on a low calorie diet with <3% weight loss.

**Rationale:** Recent advances on the **understanding of bariatric surgery** suggest that bile acids play a role in the surgery-related improvement of diabetes. RYGB is associated with doubling of the concentration of serum bile acids, and an increase in serum adiponectin and GLP-1. In rodents, BA delivered to the ileum induces weight loss and improves glucose homeostasis. These results are mainly mediated by the BA receptor, GPBAR1 (also known as TGR5). GPBAR1 stimulation results in a rapid increase in incretins, reduced appetite and improvement in insulin sensitivity. However, the role of bile acids and the key components of the bile acid pathway and enterohepatic circulation have not been elucidated in individuals with obesity.

**Preliminary data:** We recently identified a GPBAR1 gene variant associated with lower BMI, higher satiation (reduced food intake) and higher GLP-1 concentration; and demonstrated that obesity is associated with decreased fasting fibroblast growth factor 19 (FGF-19), a surrogate of ileal BA reabsorption. Interestingly, in mice, the BA effect on GLP-1 secretion is blunted in the absence of GPBAR1.

**Aim:** 1a) To characterize the bile acid pathway, key elements of the enterohepatic bile acid regulation and incretin pathway in obesity compared to health (normal weight) at three different metabolic stages: 1) at

baseline, 2) stimulated by 100 grams of fat diet (standard, validated diet for testing bile acids) and 3) on a low calorie diet with <3% weight loss.

**Experimental design:** We screen up to 45 participants and will study a total of 38 participants[ 14 individuals with a normal weight (BMI 18.5-25), 24 individuals with obesity (BMI >30)] to compare bile acid pathway, key elements of the enterohepatic bile acid regulation and incretin pathway in obesity compare to health (normal weight) at three different metabolic stages: 1) at baseline, 2) on a 100 grams of fat diet, or 3) on a low calorie, low fat diet. Participants will be on each diet for one week prior to collection of samples; with one week on regular diet between the high fat/high calorie diet and the low calorie diet. Diet will be provided by the metabolic kitchen. Participants will present after an overnight fast to the CRTU on day 5 and day 7 for testing. On day 5 participants will undergo a flexible sigmoidoscopy procedure from which a biopsy will be obtained. A bowel cleansing with water enema will be given by a CRTU nurse before the procedure. On day 7, participants will consume their "scheduled meal" and blood samples will be collected at -15, 0, 15, 30, 45, 60, 90, 120, 150, 180, 210, 240, 300, 360 minutes. Fasting and postprandial blood samples will be used to analyze, metabolomics, PYY, GLP-1, FGF-19, C4, BA, and short-chain fatty acids (SCFA). Plasma will be collected to analyze EV. Fasting saliva sample will be collected for GI peptide and metabolomics. VAS ratings of appetite and satiation will be recorded during the day every 15 minutes for the first 90 minutes, then every 30 minutes. Prior to discharge from the CRTU, participants will meet with study staff to discuss the following week's diet. On day 5 and 6 (48 hours), stool from every bowel movement will be collected for fecal BA, SCFA and microbiome. Participants will repeat the studies for a total of three times.

**Participants (Inclusion and exclusion criteria):** Through the use of a natural language processing tool and the electronic medical records, we have an established database of ~1000 patients with obesity and no other comorbidities who reside within ~100 miles, and have been evaluated at Mayo Clinic in Rochester, Minnesota. Many of them have participated in our previous studies. The specific inclusion criteria for aim 1a includes: individuals with normal weight (BMI 18.5-25), or obesity (BMI >30); these will be otherwise healthy individuals with no unstable psychiatric disease and not currently on treatment for cardiac, pulmonary, gastrointestinal, hepatic, renal, hematological, neurological, or endocrine disorders.

Days	Week 1							Week 2							Week 3							Week 4							
	0	1	2	3	4	5	6	7	1	2	3	4	5	6	7	1	2	3	4	5	6	7	1	2	3	4	5	6	7
Diet	Screen visit	Baseline							High calorie / High fat							Baseline							Low calorie / low fat						
Stool BA		X X							X X														X X						
C4-GI peptides		X							X							X													
Flex Sig		X							X														X						

## METHODS

**Participants:** Eligible subjects will be invited to participate by letter. All subjects will be given a verbal explanation of the study, provided time to read and study the written consent form and its information, given opportunities to ask questions and a copy of the consent form. Participants will be informed of their right to withdraw from the study at any time without prejudice to their clinical management now or in the future. Consent will be sought by one of the medical doctor investigators or the study coordinator, and consent will be documented by the participant's signature on the consent form. All recruitment or contact information will be approved by Mayo's Institutional Review Board.

The common inclusion criteria include:

- Age: 18-65 years.
- Gender: Men or women. Women of childbearing potential will have negative pregnancy tests within 48 hours of enrolment.
- BMI: 18.5-25, or  $\geq 30$

The common exclusion criteria include:

- a) History of abdominal surgery including cholecystectomy and other than appendectomy, Caesarian section or tubal ligation.
- b) Positive history of chronic gastrointestinal diseases, or systemic disease that could affect gastrointestinal motility, or use of medications that may alter gastrointestinal motility, appetite or absorption, e.g., orlistat, phentermine.
- c) Significant untreated psychiatric dysfunction based upon screening with the Hospital Anxiety and Depression Inventory (HAD), a self-administered alcoholism screening test (AUDIT-C) and the Questionnaire on Eating and Weight Patterns (binge eating disorders and bulimia). If such a dysfunction is identified by a HAD score  $>11$  or difficulties with substance or eating disorders, the participant will be excluded and given a referral letter to his/her primary care doctor for further appraisal and follow-up. The AUDIT-C is a 3-item alcohol screening questionnaire that reliably identifies participants who are hazardous alcohol drinkers or have active alcohol use disorders. In men, a score of 4 or more is above the recommended limits will be reviewed by study personnel. In women, a score of 3 or more is above the recommended limits will be reviewed by study personnel. However when the points are above recommended limits, the provider will review the patient's alcohol intake over the past few months to confirm accuracy and determine study eligibility.
- d) Intake of medication, whether prescribed or over the counter (except multivitamins), within 7 days of the study. Exceptions are birth control pill, estrogen replacement therapy, and thyroxin replacement therapy.

Participant activities:

- a) if recruited for the investigation participants will be asked to refrain from donating blood; refrain from participating in other research studies; avoid taking any additional over the counter or prescription medications or herbal supplements that have not been reviewed and approved by the physician or the study coordinator until the study has been completed

**Screening Visit:** Height, weight, waist measurement, hip measurement, and vital signs (pulse, blood pressure, respiration rate, and temperature) will be measured. A physical exam and medical history will be completed with the study physician. A urine sample will be collected for a pregnancy test, if applicable. The results from the test must be negative for participant to continue with the study. Subjects will also meet with a dietitian to review food preference and allergies.

**Visit 2, 4, 7:** These visits occur on 'day 5' of each week. An un-sedated flexible sigmoidoscopy with prior tap water enema will be performed, with a biopsy of the sigmoid colon (n=8) and rectum (n=8).

**Visit 3, 5, 8:** These visits are 'day 7' of each week. Vital sign, height, weight, waist circumference and hip circumference will be taken. Subjects will be fed a meal that matches the macronutrient make-up of the week. During visit 3, the baseline week, they will be fed a standard CRTU breakfast and lunch. Fasting saliva and blood will be drawn as listed above. VAS ratings of appetite and satiation will be recorded. Before leaving on visits 3 and 5, participants will meet with the study staff.

**Visit 6:** This visit will occur during week 3. It involves meeting with a study staff regarding week 4 of the investigational study diet.

**Diet:** During weeks 1 (baseline) and 3 (stabilization), participants will have a daily food diary; The total daily intake of calories and macronutrients will be calculated by our team's registered dietitian. For weeks 2 and 4, we will provide every meal to the participants. The 100 grams of fat diet will consist of 2700 kcal, 100g total fat (33%), 300mg cholesterol, 350g carbohydrates (52%), and 100g protein (15%). The low calorie, low fat diet will consist of 1200 kcal, 26g fat (20%), 78mg cholesterol, 150g carbohydrates (50%), and 100g protein (30%). Meals will be provided by the metabolic kitchen. All uneaten food will be returned to the metabolic kitchen and weighed to determine exact food consumption.

**Blood Samples:** Fasting and postprandial blood samples will be collected by standard techniques and stored in a  $-70^{\circ}\text{C}$  freezer in our laboratory. DNA will be obtained and stored for future studies.

**Saliva Samples:** fasting saliva samples will be collected by standard techniques and stored in a  $-70^{\circ}\text{C}$  freezer in our laboratory. Future studies will include metabolomics and GI peptides.

**Collection of Fecal Sample for Fecal Organic Acids:** HPLC-tandem MS will be utilized to identify, characterize and quantify total and individual fecal BAs. The 48-hour stool collection will be weighed and divided into aliquots. Samples will then be analyzed for total fat (routine Van de Kamer method at Mayo Medical Laboratory), total BAs, and primary and secondary BAs [by LC/MS as previously described by our group (Shin, 2013b)]. Additional stool samples will be stored for future microbiome studies.

**Serum 7 $\alpha$ -hydroxy-4-cholest-3-one (C4)** will be measured based on the method adapted from Galman et al. and using HPLC-tandem mass spectrometry.

**Serum FGF-19** levels will be measured by enzyme-linked immunosorbent assay (FGF-19 Quantikine ELISA Kit; R&D Systems, Minneapolis, MN).

**Plasma gastrointestinal hormones (GLP-1 and PYY)** levels will be measured by radioimmunoassay (Linco Research, Inc., St. Charles, MO).

**Metabolomics:** We will perform quantitative, targeted metabolomics of salient classes of compounds and untargeted metabolomics in plasma and saliva samples using mass spectrometry. These assays are well-established, validated, and routinely performed in the Mayo Clinic Metabolomics Core Laboratory.

**Microbiome:** Stool aliquots will be frozen at -70°C freezer in our laboratory for future microbiome studies.

**Plasma extracellular vesicles** will be analyzed based on the method adapted from Witwer et al. and stored in a -70°C freezer

**Flexible sigmoidoscopy** will be performed in the CRTU, with a prior tap water enema by the CRTU nurse. Using standard biopsy forceps, 16 mucosal biopsies will be obtained each from the sigmoid colon and the rectum. Eight biopsies will provide adequate tissue for microbial DNA extraction. If any abnormality is seen on sigmoidoscopy, additional biopsies will be obtained for histology. The colonic mucosal microbiota will be compared to that evaluated with a rectal catheter.

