## STATISTICAL ANALYSIS

**Endpoints:** *Primary endpoint:* Fecal BA excretion in obesity vs. health and the change from baseline with high fat/high calorie diet vs. low calorie diet. *Secondary endpoints:* (a) fecal individual BA and SCFA excretion; (b) fasting serum C4 and FGF19; (c) serum BA; and (d) serum fasting, peak and AUC postprandial FGF-19, GLP-1 and PYY.

**Statistical analysis:** The proposed analyses are based on analysis of covariance models, with the responses being each variable compared to baseline. The covariates to be considered include gender and BMI.

**Sample size:** In healthy volunteers, the normal value for fecal BA is  $957 \pm 185$  micromoles/48hours (SEM). The table below summarizes data for primary endpoint considering the mean difference between two groups (healthy vs. obesity) and difference between baseline to high fat vs. low fat diet in each group (healthy vs. obesity), n=8 per group; and estimates the effect size detectable with 80% power based on a two sample t-test at a two-sided  $\alpha$  level of 0.05. We will accrue 38 participants to achieve the above given n value, assuming a 20% dropout rate.

Response	Mean	SD	Predicted differences [% (absolute #)] n=8/group
Fecal BA, $\mu$ moles/48hours	957	185	1) Patient with obesity compared to health: 25% (258 $\mu$ moles/48h) 2) Baseline compared to high fat vs. low fat diet: 24% (233 $\mu$ moles/48h)

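### One 7-day medication look-back, with no antibiotic or probiotic rule, lets recovery of the gut flora be counted as a diet effect on individual fecal bile acids and SCFA

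*Combined protocol and SAP*

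**What the plan says.** Exclusion d) in METHODS bars "Intake of medication, whether prescribed or over the counter (except multivitamins), within 7 days of the study". Its carve-outs are all permissive: "Exceptions are birth control pill, estrogen replacement therapy, and thyroxin replacement therapy". No drug class has a longer window, and the protocol does not say whether the 7 days run back from screening or from the first diet day.

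Three other rules touch on medication:

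- Exclusion b) in METHODS covers "use of medications that may alter gastrointestinal motility, appetite or absorption, e.g., orlistat, phentermine". It states no time window and does not mention colonic bacteria.
- The health criterion in APPROACH requires people to be "not currently on treatment for cardiac, pulmonary, gastrointestinal, hepatic, renal, hematological, neurological, or endocrine disorders", so a completed course does not breach it.
- Under participant activities in METHODS, recruited participants must "avoid taking any additional over the counter or prescription medications or herbal supplements that have not been reviewed and approved". This looks forward only.

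On the measurement side, the INTRODUCTION says that bile acid escaping reabsorption is "deconjugated and dehydroxylated by colonic bacteria into secondary BA and then excreted in the stool". METHODS assays total, primary and secondary fecal bile acids. STATISTICAL ANALYSIS lists "fecal individual BA and SCFA excretion" as secondary endpoint (a). Responses are compared with baseline in covariance models, and the covariates to be considered include only gender and BMI.

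**The concern.** The eligibility rules guard against drugs that change motility, appetite or absorption. They have no specific rule for the drugs that act directly on the bacteria which, by the protocol's own account, produce part of what endpoint (a) measures.

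The schedule gives the gap a direction. Everyone goes through baseline, high fat, usual diet and low calorie in that order, so baseline is always the sample closest to any earlier antibiotic course. If bacterial function is still returning in week 1, the return appears as change from baseline. Comparing with baseline does not remove the problem, because baseline is the disturbed measurement. No model term or exposure record would allow it to be separated from diet afterwards.

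**Working it through.** The plan gives no figure to reproduce here. The check is a reading of the criteria, a day count and a count under stated assumptions.

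**1. Is the person eligible?** Take a last antibiotic dose 8 days before day 1 of week 1. Exclusion d) is met, since 8 > 7. Exclusion b) is not written as an antibiotic rule, though it could catch a particular antibiotic judged to alter motility or absorption. The health criterion concerns current treatment, and the participant rule is prospective. The person can be enrolled. For probiotics it is not even clear that they count as medication under d).

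**2. When is stool collected?** Stool is taken on days 5 and 6 of weeks 1, 2 and 4. Days since last dose = 8 + (study day - 1).

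- Week 1, study days 5-6: 12-13 days.
- Week 2, study days 12-13: 19-20 days.
- Week 4, study days 26-27: 33-34 days.

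If the 7 days run back from screening on day 0 and day 1 is the next day, each interval is one day longer. The change from baseline to week 4 spans 21 days of possible recovery (33 - 12), and the change from baseline to week 2 spans 7. In a direct comparison of the two diets the shared baseline cancels, but 14 days of recovery (33 - 19) remain.

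**3. How many people?** The documents give neither antibiotic use nor recovery time. Assumptions: 5-15% had a course in the preceding 60-90 days, end dates are evenly spread, and recovery takes 4-12 weeks. Expected users among 38: 0.05 x 38 = 1.9 to 0.15 x 38 = 5.7.

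A course ending x days before day 1 is x + 4 days old when baseline stool collection starts. It counts if x is at least 8 (eligible) and x + 4 does not exceed the recovery time (still recovering).

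- Recovery 28 days: x = 8 to 24, which is 17 days.
- Recovery 84 days: x = 8 to 80, which is 73 days, or 8 to 60 (53 days) where the use figure covers only 60 days.

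| Use | Period | Recovery 4 weeks | Recovery 12 weeks |
|---|---|---|---|
| 5% | 90 days | 1.9 x 17/90 = 0.4 | 1.9 x 73/90 = 1.5 |
| 5% | 60 days | 1.9 x 17/60 = 0.5 | 1.9 x 53/60 = 1.7 |
| 15% | 90 days | 5.7 x 17/90 = 1.1 | 5.7 x 73/90 = 4.6 |
| 15% | 60 days | 5.7 x 17/60 = 1.6 | 5.7 x 53/60 = 5.0 |

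The range is about 0.4 to 5 of 38. It counts only courses inside the period to which the use figure applies.

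**4. What does that do to a mean?** If each affected person's change is shifted by b, the overall mean change shifts by (number affected / 38) x b: 0.4/38 = 1% to 5/38 = 13% of b. One such person moves the mean of the 24 with obesity by b/24 (4%) and the mean of the 14 with normal weight by b/14 (7%). The documents give no value for b, so the bias itself cannot be calculated.

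**The case against.** The strongest reply is that this is a small exploratory study in otherwise healthy people. Recent antibiotic use may be rarer than assumed, and the screening medical history with the study physician already offers a chance to ask. At the short end of the recovery range fewer than two participants are affected. That stands as a limit on size. It does not close the gap, because no criterion tells staff to exclude or record such use.

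Several stronger readings are tempting, and the documents do not support them:

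- **Every recent antibiotic user is disturbed at baseline.** This fails at 4-week recovery, where only 17 of 60 to 90 days count (19-28%). Some users also finished within 7 days and are already excluded.
- **The primary endpoint is biased.** The protocol says bacteria convert bile acids. It does not say that conversion changes the total excreted.
- **The obesity-versus-health contrast is biased.** Nothing shows that antibiotic use differs between the groups. Without a difference, the effect on that contrast is mainly added noise.
- **The microbiome results are compromised.** Stool for microbiome work is only banked for later studies. The protocol does say "Eight biopsies will provide adequate tissue for microbial DNA extraction", but the comparison it describes is mucosal sampling against a rectal catheter, which compares sampling methods. No bias in that comparison has been shown.
- **Recent appetite-drug users can enter in the same way.** Exclusion b) has no time limit and can be read as covering past use. If it meant only the past week, d) would make its drug clause redundant.

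**Conclusion.** The concern holds for secondary endpoint (a), in its change from baseline. The 7-day rule admits people with recently completed antibiotic courses, the endpoint depends partly on colonic bacteria by the protocol's own account, and the fixed diet order makes recovery run in the same direction as study time.

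The size is modest and conditional: about 0.4 to 5 of 38 participants, given assumed use of 5-15% over 2-3 months and assumed recovery of 4-12 weeks. The eligibility gap and the sampling days come from the text, with day 1 assumed as the reference for the 7 days. The use rate, the recovery time and the per-person shift do not. This is an inexpensive improvement to a stated rule and does not put the main comparison in doubt.

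**What to change.** Keep the 7-day general window in exclusion d) and state the day from which it runs. Then:

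1. Add a separate, longer look-back before week 1 for completed courses of systemic antibiotics and for probiotics. About 4 weeks is a working assumption, and the investigators should justify the length they choose.
2. Apply it only to people who have already finished, so that nobody stops a treatment in order to qualify. Allow re-screening once the window has passed.
3. Record recent and in-study antibiotic and probiotic use for every participant.
4. Pre-specify a repeat of the endpoint (a) analysis without exposed participants.

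The cost is a line of eligibility text, a screening question, a data field and a sensitivity analysis. The plan has 45 - 38 = 7 spare screens. Under the same use assumptions, a 4-week antibiotic rule newly defers people whose course ended 8-28 days before day 1 (21 days): 45 x 0.05 x 21/90 = 0.5 to 45 x 0.15 x 21/60 = 2.4 of 45. Probiotic users would come on top, and the documents give no basis for counting them. A 3-month rule would touch 45 x 0.05 = 2 to 45 x 0.15 = 7 people, possibly the whole margin, and nothing in the documents supports that length.

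Four weeks does not cover slow recovery. At 12 weeks and 15% use, about 5.7 x 32/60 = 3.0 (courses ending 29-60 days before) to 5.7 x 52/90 = 3.3 (29-80 days before) would remain. The exposure record and the repeat analysis are therefore needed as well as the window, and the record should reach back further than the window does.
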